4. STUDY DESIGN

4.1 Overall Design

This is a single-centre, follow-up, observational, cross-sectional study of four distinct, longitudinal cohorts. Extensive clinical history will be obtained from each participant, and symptom questionnaire characterisation of Long-COVID (with a strong focus on organ-specific dysfunction, psychiatric, sleep, and pain parameters – all of which appear to be major features of Long-COVID), as well as laboratory and genetic characterisation will be performed. A subset of each cohort will be randomly selected for more specific syndrome characterisation related to sleep and pain, respiratory, cardiology, renal and glucose metabolism.

The consequences of Long-COVID will be described and compared in four large, well-described clinical cohorts of African patients surviving SARS-CoV-2:

- Cohort 1: asymptomatic subjects found to be PCR/antigen/antibody-positive during routine screening for SARS-CoV-2 infection

- Cohort 2: symptomatic outpatients who were confirmed to have COVID-19 through a positive PCR/antigen test
- Cohort 3: inpatients surviving hospitalisation for severe COVID-19 and who were PCR/antigen-positive
- Cohort 4: participants vaccinated in clinical trials in 2020 prior to widespread community exposure, and hence protected from severe COVID-19 (and possibly Long-COVID) if subsequently infected.

After obtaining informed consent from potential participants, a single cross-sectional, baseline visit will be conducted for each participant. Demographic data, clinical history (including COVID-19 history, targeted symptoms, and risk factors), COVID-19 vaccination dates (if administered), and details of previous and concomitant medications will be collected. Multiple questionnaires related to psychiatric screening, psychosocial factors, work function assessment, sleep quality, and pain assessment will be administered. Respiratory and cardiac function will be evaluated through a dyspnoea scale, walking test and an ECG. Laboratory evaluations will include a full blood count, serum chemistry, liver function tests, renal function assessment, inflammatory markers, and DNA extraction for genotyping. Blood and urine samples will be stored locally for possible future analysis. Human immunodeficiency virus (HIV) testing will be performed for participants consenting to this optional assessment.

After the baseline visit, participants with Long-COVID will be identified using the WHO clinical definition and general health assessments [2]. Randomly selected sub-groups of participants with, and without, Long-COVID will be selected from each of the four cohorts for additional investigations through participation in the following sub-studies:

- Respiratory evaluation: dyspnoea assessment, high-resolution computed tomography (CT) scan, lung function studies including spirometry and diffusion capacity (DLCO) [Section 7.2.2.1]
- Cardiac evaluation: clinical history and examination, serial blood pressure, six minute walk test (distance), ECG, echocardiogram including speckle tracking, cardiac magnetic resonance imaging (MRI), creatine kinase MB fraction (CK-MB), cardiac troponin T (cTnT), prohormone brain natriuretic peptide (pro-BNP), and possible coronary angiography in patients with acute coronary syndromes and unstable angina [Section 7.2.2.2]
- Psychiatric and neuroendocrine evaluation: questionnaires/surveys, semi-structured interview, home visit, saliva cortisol analysis, collection of diary data, actigraphy, adrenocorticotrophic hormone (ACTH) challenge (cosyntropin sensitivity test [CST]), cellular immunity assessment [Section 7.2.2.3]
- Sleep evaluation: questionnaires, actigraphy with sleep diaries, polysomnography (PSN) [Section 7.2.2.4]
- Pain evaluation: quantitative sensory testing (QST) and conditioned pain modulation (CPM) assessments [Section 7.2.2.5]
- Glucose metabolism evaluation: oral glucose tolerance test (OGTT) including assessment of glucose, insulin, and c-peptide to estimate insulin sensitivity and beta-cell function [16]. [Section 7.2.2.6]

Abnormalities detected in the assessments (including undiagnosed mental health issues) will be managed by on-study medical personnel with referral as appropriate.

4.2 Study Treatments

No treatment will be administered during this observational study. Participants taking medication(s) at the time of screening and enrolment, will continue to take this throughout their participation in the study.

4.3 Study Duration

The duration of participation for each participant will either be a single visit (of approximately 6 hours), or two or more visits depending on whether they are enrolled into any sub-studies.

Total duration for each participant will be up to 6 months depending on sub-study enrolment.

Participants selected for the sleep study will have an overnight admission at the University of the Witwatersrand (Wits) Faculty of Health Sciences sleep laboratory.

4.4 Individual Participant Withdrawal

A participant may be withdrawn from the study for any of the following reasons:

- At the request of the participant (withdrawal of informed consent), irrespective of the reason for this
- At the request of the primary care provider if he or she thinks the study is not in the best interest of the participant
- At the discretion of the Investigator if he or she believes that continuation in the study would be detrimental to the participant's well-being in any way, or
- At the discretion of the Institutional Review Board/Ethics Committee if they believe that continuation in the study would be detrimental to the participant's well-being in any way.

Participants will be considered withdrawn if they state an intention to withdraw, fail to return for visits, or are lost to follow-up for any other reason. For participants who are lost to follow-up, the Investigator will attempt to trace the participant, and will demonstrate "due diligence" by documenting all steps taken to contact the participant (e.g., dates of telephone calls, home visit, etc.) in the source documents.

If a participant withdraws consent for disclosure of future information, the Sponsor may retain and continue to use any data collected before such withdrawal of consent.

If a participant withdraws from the study, he or she may request destruction of any samples taken and not tested. This must be documented by the Investigator in the site study records.

Participants who withdraw or are withdrawn will not be replaced.

5. STUDY POPULATION

Adults at least 18 years of age with previous confirmed SARS-CoV-2 infection (symptomatic or asymptomatic) will be invited to participate. Approximately 400 participants will be enrolled.

5.1 Cohorts

The following well-described cohorts of participants will be enrolled (approximately 100 participants in each):

- Cohort 1: participants who were asymptomatic but were found to be SARS-CoV-2 PCR/antigen/antibody-positive during routine screening previously

- Cohort 2: participants who were previous outpatients with symptomatic COVID-19 confirmed through a positive SARS-CoV-2 PCR/antigen test
- Cohort 3: participants who were previous inpatients and survived hospitalisation for severe COVID-19 confirmed through a positive SARS-CoV-2 PCR/antigen test
- Cohort 4: participants who were previously infected with SARS-CoV-2 (symptomatic or asymptomatic) confirmed through a positive PCR/antigen/antibody test after being vaccinated in a non-placebo arm of a SARS-CoV-2 vaccine trial in 2020, with a vaccine demonstrated to be effective against severe COVID-19.

Participants enrolled in early vaccine trials were screened out if they were concurrently infected with SARS-CoV-2 as detected through a minimum of PCR testing. Given that they were only exposed to the first wave of COVID-19 infections in South Africa during which severe lock-down measures were in place, the probability of them being infected with SARS-CoV-2 prior to vaccination would have been low.

5.2 Recruitment

Potential participants may volunteer in response to advertised clinical trial information, or will be contacted in compliance with POPIA regulations and invited to participate in the informed consent process (Section 11.2) and attend the baseline visit. Written informed consent will be obtained prior to any screening, and study-specific assessments and procedures. The following platforms will be used to identify potential participants:

- Cohort 1:
 - Volunteers who had previous asymptomatic SARS-CoV-2 infection confirmed by a documented positive PCR/antigen/antibody test during routine screening (e.g. for travel, elective surgery or as part of contact tracing)
 - Participants enrolled into prophylaxis studies who had a documented PCR/antigen/antibody-positive test during routine screening but no symptoms of infection
 - Participants enrolled in self-sampling and antigen evaluation protocols with documentation of a positive PCR/antigen test during routine screening but no symptoms of infection.
- Cohort 2:
 - Volunteers who had previous symptomatic COVID-19 confirmed by a documented positive PCR/antigen test, and who were managed as outpatients
 - Participants enrolled in large, early treatment, antiviral studies in symptomatic outpatients
 - Participants enrolled into prophylaxis studies who developed symptoms of infection confirmed to be COVID-19 through a documented positive SARS-CoV-2 PCR/antigen test at the time
 - Participants enrolled in self-sampling and antigen evaluation protocols who developed symptoms of infection confirmed to be COVID-19 through a documented positive SARS-CoV-2 PCR/antigen test.
- Cohort 3:
 - Age- and gender-matched patients treated at the Helen Joseph Hospital and Charlotte Maxeke Johannesburg Academic Hospital Infectious Diseases department who were infected at approximately the same time as participants recruited for Cohorts 1 and 2.

- Cohort 4:

- Participants enrolled in a non-placebo arm of a COVID-19 vaccine trial who received a vaccine that has subsequently been proven to be effective, and who were subsequently confirmed to be infected with SARS-CoV-2 (symptomatic or asymptomatic) through a documented positive PCR/antigen/antibody test.

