3. OBJECTIVES AND ENDPOINTS

Primary	
Objectives	Endpoints
To characterise Long-COVID in four cohorts of patients with previous SARS-CoV-2 infection (asymptomatic, symptomatic, severely symptomatic requiring hospitalisation, and those who were vaccinated prior to widespread community exposure).	Incidence, severity, and duration of Long-COVID symptoms.
Secondary	
Objectives	Endpoints
To describe the following characteristics in four cohorts of patients with previous SARS-CoV-2 infection (asymptomatic, symptomatic, severely symptomatic requiring hospitalisation, and those who were vaccinated prior to widespread community exposure): 
• Inflammatory markers• Psychological profiles• Psychosocial exposures• Work performance in employed participants	
• High sensitivity C-reactive protein (hs-CRP)• Interleukin-1β (IL-1β)• Interleukin-6 (IL-6)• Interleukin-8 (IL-8)• Tumour necrosis factor alpha (TNFα)• Tumour necrosis factor alpha receptor-1 (TNFR1)• Monocyte chemoattractant protein-1 (MCP-1)• Headache Impact Test-6 (HIT-6)• Patient Health Questionnaire-9• Generalised Anxiety Disorder 7• PTSD Checklist for DSM-5 - Civilian Version• Mood Disorder Questionnaire• Montreal Cognitive Assessment• Daily Fatigue Impact Scale• COVID-19 related stress questionnaire• Multidimensional Scale of Perceived Social Support• Perceived Stress Scale• Adverse Childhood Experiences tool• Normal activities and work productivity questionnaire

• Sleep quality and disorders• Pain experience• Cardiorespiratory function• Standard laboratory parameters• Renal function• Host genetic factors that may be associated with Long-COVID	
• Pittsburgh Sleep Quality Index• Epworth Sleepiness Scale• Berlin Questionnaire for risk of sleep apnoea• International Restless Legs Syndrome Severity Scale• Sleep quality and mood visual analogue scale• Brief Pain Inventory• Modified Medical Research Council (mMRC) Dyspnoea Scale• Six-minute walk test (distance)• Electrocardiogram (ECG) parameters and morphology• Full blood count• Serum chemistry• Liver function tests• Glucose, glycosylated haemoglobin (HbA1C)• Creatinine clearance• Cystatin-C• Urine dipstick parameters• Urine albumin-to-creatinine ratio• Genotyping results• DNA sequencing results
Exploratory Objectives	

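### Volunteers are a listed source for Cohorts 1 and 2 only, and recruitment route is not among the data to be collected, so a route effect on Long-COVID frequency could not be told from a cohort effect

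*Protocol*

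**What the plan says.** Protocol Section 5.2 begins with a statement that is not tied to any cohort: "Potential participants may volunteer in response to advertised clinical trial information", or they are contacted under the data-protection rules and invited. It then lists sources cohort by cohort.

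- **Cohort 1**, three sources. The first is "Volunteers who had previous asymptomatic SARS-CoV-2 infection confirmed by a documented positive PCR/antigen/antibody test during routine screening". The other two are rosters, for example "Participants enrolled into prophylaxis studies who had a documented PCR/antigen/antibody-positive test during routine screening but no symptoms of infection"; the third is self-sampling and antigen evaluation protocols.
- **Cohort 2**, four sources. The first is "Volunteers who had previous symptomatic COVID-19 confirmed by a documented positive PCR/antigen test, and who were managed as outpatients". The other three are rosters of antiviral, prophylaxis and self-sampling studies.
- **Cohort 3**: patients of two named hospitals, matched on age and gender and infected at about the same time as Cohorts 1 and 2. There is no volunteer line.
- **Cohort 4**: recipients of active vaccine in COVID-19 vaccine trials. There is no volunteer line.

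No quota or cap on volunteers is given. The primary endpoint (Section 3) is "Incidence, severity, and duration of Long-COVID symptoms". Section 4.1 states: "The consequences of Long-COVID will be described and compared in four large, well-described clinical cohorts of African patients surviving SARS-CoV-2". Section 9.2.2 plans descriptive summaries overall, per cohort and per disease status.

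The screening data (Section 7.1.1) cover test, illness, hospitalisation and vaccination dates. The demographic and social data (Section 7.1.2.1) do not include how the participant came to the study. Section 9.2.2 names time since infection, vaccination, repurposed medicines, and undisclosed vaccination or infection as factors to account for. It does not name recruitment route.

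**The concern.** The study is about persistent symptoms and offers an extensive work-up with feedback and referral. It is plausible that someone who still has symptoms is readier to answer its advertisement than someone who has recovered. Selection of that kind acts on the primary outcome itself, so adjusting for time since infection or vaccination would not remove it. Nor would the matching of Cohort 3 on age, gender and infection period.

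Because the volunteer line appears only for the two non-hospitalised infection cohorts, the effect, if present, would raise their Long-COVID frequency relative to Cohorts 3 and 4. A per-cohort summary alone cannot separate that from a real cohort difference. An analysis plan can only use route if route has been captured, so this has to be settled in data collection.

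**Working it through.** The protocol states no expected frequency, volunteer share or effect size, so there is no planned figure to reproduce. The only input it supplies is 100 participants per cohort (Synopsis, Sample Size). The rest is assumption, used to show scale.

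**Inputs**
- n = 100 per cohort (protocol).
- p = true Long-COVID frequency in the source population; 30% assumed.
- r = how many times as likely people with Long-COVID are to volunteer as people without it; 1.5, 2 and 3 assumed.
- f = share of the cohort who are volunteers; 25%, 50% and 100% assumed. Invited participants are taken to show the true p.

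**Formulas**
- Frequency among volunteers: q = r·p / (r·p + 1 − p).
- Observed frequency in the cohort: f·q + (1 − f)·p, so the excess is f·(q − p).

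**Volunteers only, p = 0.30**
- r = 1.5: 0.45 / 1.15 = 0.391
- r = 2: 0.60 / 1.30 = 0.462
- r = 3: 0.90 / 1.60 = 0.5625

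**Excess in percentage points for the whole cohort**

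| r | f = 25% | f = 50% | f = 100% |
|---|---|---|---|
| 1.5 | 2.3 | 4.6 | 9.1 |
| 2 | 4.0 | 8.1 | 16.2 |
| 3 | 6.6 | 13.1 | 26.3 |

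**Sampling error for comparison (95%, p = 0.30)**
- One cohort of 100: 1.96·√(0.30·0.70/100) = 9.0 points.
- Difference between two cohorts of 100: 1.96·√(2·0.30·0.70/100) = 12.7 points.

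**Other true frequencies.** With r = 2 and f = 50%, the excess is 4.1, 8.1, 8.3 and 4.4 points at p = 10%, 30%, 50% and 80%. The matching half-widths for a difference are 8.3, 12.7, 13.9 and 11.1 points.

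So the bias stays inside the sampling error of a difference when volunteers are a minority to half of the cohort and r is 2 or less. At r = 3 with half volunteers it slightly exceeds it (13.1 against 12.7). Excesses of 9 to 26 points arise only if the whole cohort volunteered. At r = 1 the bias vanishes, and below 1 it changes sign. Unlike sampling error, it would not show in a confidence interval.

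**The case against.** Several points on the other side stand.

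- **Cohorts 1 and 2 are not self-selected cohorts.** Rosters are two of three listed sources for Cohort 1 and three of four for Cohort 2. A reader might infer a clean split between volunteers and lists; the section does not show one.
- **The opening sentence of Section 5.2 covers every cohort.** It does not itself show a difference, and nothing in it bars a hospital survivor or vaccine-trial participant from answering the advertisement. The evidence is in the cohort lists.
- **Invited people also choose.** They consent knowing the purpose of the study, to a visit of about six hours. If symptoms drive uptake in all cohorts, the difference between cohorts is smaller than r suggests.
- **Direction is not shown.** A broad health check with results fed back may attract people whatever their symptoms.
- **The study is exploratory and descriptive.** No test of incidence between cohorts is specified, and Section 4.1 speaks of comparing consequences of Long-COVID.
- **The analysis plan is not at hand.** The co-factor list in Section 9.2.2 is open-ended, so a table by route could still be planned. Section 11.4 also keeps notes of participant contacts, from which some routes might be reconstructed.

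The last two points do not dispose of the matter. Frequencies by cohort are a main product of a descriptive study. An analysis by route needs a defined variable for every participant, and the protocol's data lists contain none; contact notes are not a substitute for it.

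**Conclusion.** The point holds as a possible bias that the listed data would leave uncheckable. Volunteers are a listed, uncapped source for two of the four cohorts, and route is neither collected nor named as a co-factor.

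The size rests entirely on assumed p, r and f. At a true 30% with 25 to 50% volunteers, the excess is about 2 to 8 points for r between 1.5 and 2, less than the 12.7-point half-width of a difference. It is as large as that half-width or larger only under strong selection with many volunteers, or in a largely volunteer cohort.

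A reader might infer more: that the per-cohort frequencies are biased, that the gradient towards Cohort 3 would reverse, or that the analysis is unable to reveal it. The documents do not support these. They give no volunteer share, no measure of how symptoms affect volunteering and no expected Cohort 3 frequency, and they leave the choice of co-factors open. Because Cohorts 1 and 2 list both routes, the question can be examined within each of them once route is recorded.

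**What to change.** 1. Add recruitment route to the screening data in Section 7.1.1 for every participant in all four cohorts: answered an advertisement, or contacted from a list, with the list named.
2. Report the primary endpoint by route within Cohorts 1 and 2.
3. Add a sensitivity analysis of the between-cohort comparison limited to invited participants. Keep the full cohorts as the main summary.

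The cost is one eCRF field and one extra table; eligibility, sample size and procedures do not change. The sensitivity analysis is less precise. If half of a cohort are volunteers, 50 invited participants remain and the half-width for that cohort at 30% is 1.96·√(0.21/50) = 12.7 points instead of 9.0. Against a full cohort of 100, the half-width of the difference becomes 1.96·√(0.21/50 + 0.21/100) = 15.6 points instead of 12.7. That loss is why it should not replace the main summary. Self-selection among invited people would remain and should be stated as a limitation.

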5.3 Main Study Eligibility Criteria (Baseline Visit)

The following eligibility criteria will be used to select study participants for the main study (baseline visit only).

5.3.1 Inclusion criteria

1. Able and willing to provide written or electronic informed consent for the baseline visit prior to any study-specific assessment or procedure.
2. Age at least 18 years at the time of signing the informed consent form.
3. Previous asymptomatic SARS-CoV-2 infection, confirmed through a documented positive PCR, antigen, or antibody test, at least six months prior to the baseline visit **[Cohort 1 only]** or, previous symptomatic SARS-CoV-2 infection for which hospitalisation was not required, confirmed through a documented positive PCR or antigen test at the time, at least six months prior to the baseline visit **[Cohort 2 only]** or, previous hospitalisation for management and treatment of COVID-19 confirmed through a documented positive PCR or antigen test at the time, at least six months prior to the baseline visit **[Cohort 3 only]** or, previous asymptomatic or symptomatic SARS-CoV-2 infection, confirmed through a documented positive PCR, antigen, or antibody test, at least six months prior to the baseline visit and received a COVID-19 vaccine in a non-placebo arm of a COVID-19 vaccine study during 2020 **[Cohort 4 only]**.
4. Willing to consent to verification of vaccination status on the national Electronic Vaccination Data System (EVDS).
5. Access to a reliable telephone or other device permitting information transfer.

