7.1.2.2 Medical and surgical history

In addition to general information related to past and current relevant medical conditions and surgical procedures, and menstrual cycle, pregnancy and lactation status (for female participants only), the following specific information will be collected:

- COVID-19 history (for participants with previous symptomatic infection(s)) including:
 - Symptoms experienced (including cough, fatigue, fever, malaise, shortness of breath, ageusia, anosmia, and other symptoms)
 - Whether or not the participant was pregnant at the time of SARS-CoV-2 infection (female participants only)
 - Whether or not the participant required supplemental oxygen at the time of COVID-19
 - Whether or not the participant required intensive care unit (ICU) admission for COVID-19 (Cohort 3 only)
 - Whether or not the participant required mechanical ventilation for COVID-19 (Cohort 3 only)
- Long-COVID symptom-directed history to gather information about symptoms not assessed through the detailed questionnaires and surveys listed in Sections 7.1.2.5 to 7.1.2.6.

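### Inclusion criterion 3 is looser than the definitions of Cohorts 3 and 4, and ICU and ventilation data are not collected for hospitalised participants in Cohort 4

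*Protocol*

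**What the plan says.** Section 5.1 describes Cohort 3 as "participants who were previous inpatients and survived hospitalisation for severe COVID-19 confirmed through a positive SARS-CoV-2 PCR/antigen test". It restricts Cohort 4 to people infected after vaccination in an active arm of a 2020 trial "with a vaccine demonstrated to be effective against severe COVID-19". Section 5.2 describes the Cohort 4 recruitment source as people "who received a vaccine that has subsequently been proven to be effective", without mention of severe disease.

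Section 5.3 then states: "The following eligibility criteria will be used to select study participants for the main study (baseline visit only". Criterion 3 in 5.3.1 asks, for Cohort 3, for "previous hospitalisation for management and treatment of COVID-19 confirmed through a documented positive PCR or antigen test at the time", and for Cohort 4 that the person "received a COVID-19 vaccine in a non-placebo arm of a COVID-19 vaccine study during 2020". The synopsis carries the same wording for both.

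Section 7.1.2.2 records, for anyone with a past symptomatic infection, "Whether or not the participant required supplemental oxygen at the time of COVID-19". ICU admission and mechanical ventilation are listed for Cohort 3 only. Section 7.1.1 collects vaccination dates and hospitalisation dates and duration at screening; it does not list the vaccine product.

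**The concern.** The four cohorts are the comparison structure of the study. Section 4.1 says the consequences of Long-COVID will be described and compared across them, and Section 9.2.2 summarises every primary and secondary endpoint by cohort. What a cohort label means therefore decides what its results can be said to show.

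Two labels carry more than the selecting text delivers. Section 4.1 interprets Cohort 4 as vaccinated "and hence protected from severe COVID-19 (and possibly Long-COVID) if subsequently infected", which depends on the product. Cohort 3 is called severe in Sections 4.1 and 5.1, yet criterion 3 contains no marker of severity beyond admission. If some admissions were not severe, the contrast between Cohorts 3 and 2 could shrink and the label would mislead.

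The limit on the ICU and ventilation items has a separate consequence. Severe infection in a vaccinated participant is the outcome that would test the premise of protection, and these two markers of it would not be collected in Cohort 4.

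**Working it through.** The protocol gives no sample-size derivation, power or expected rate, so there is no figure to reproduce. The check is a comparison of text.

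| Source | Cohort 3 | Cohort 4 |
|---|---|---|
| 4.1 | inpatients, severe disease | 2020 trial vaccinees, taken as protected |
| 5.1 | inpatients, severe disease | vaccine shown effective against severe disease |
| 5.2 | patients treated at two named hospitals; no severity condition | vaccine proven effective |
| 5.3.1 and synopsis, criterion 3 | any admission to manage and treat COVID-19 | any COVID-19 vaccine, active arm, 2020 |
| 5.3.2 exclusions | nothing on severity | no infection before vaccination; nothing on product |
| Section 3 objectives | severe symptoms needing admission | vaccinated before widespread exposure |

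**Cohort 4.** Three sections state three different conditions on the vaccine, and the loosest is in the criteria that select participants. No exclusion restores the missing condition. Section 5.2 serves to identify potential participants and also allows volunteers who answer advertisements, so it does not replace an eligibility criterion. Since 7.1.1 lists vaccination dates only, a condition on the product could not be checked from the listed screening data.

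**Cohort 3.** Criterion 3 separates Cohorts 2 and 3 by whether hospitalisation was needed. The word severe appears in 4.1 and 5.1, but the protocol gives no threshold for it. The mismatch is therefore between an undefined label and a clear admission criterion.

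**ICU and ventilation.** Criterion 3 lets Cohort 4 include symptomatic infection, and no exclusion removes hospitalised cases. A hospitalised person enrolled in Cohort 4 would have admission dates and the oxygen answer on record, but neither ICU nor ventilation.

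**Illustration of dilution in Cohort 3, on assumed rates.** Let f be the share of Cohort 3 whose admission was not severe, p3 the Long-COVID frequency after severe admission and p2 that in Cohort 2. Assume non-severe admissions behave like Cohort 2. Then

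expected difference = [(1 − f) × p3 + f × p2] − p2 = (1 − f) × (p3 − p2).

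- With p3 = 50% and p2 = 30%, the difference is 20 points at f = 0, then 0.9 × 20 = 18 at f = 10%, 0.8 × 20 = 16 at 20%, 0.7 × 20 = 14 at 30% and 0.6 × 20 = 12 at 40%.
- With p3 = 60% and p2 = 30%, it falls from 30 points at f = 0 to 0.6 × 30 = 18 at f = 40%.

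None of p3, p2 or f is in the protocol. The formula shows only that any shrinkage is proportional to f. No similar calculation is offered for Cohort 4, which mixes asymptomatic and symptomatic infection by design, so the documents fix no direction.

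**The case against.** The best reply for Cohort 3 is that no threshold was dropped. The objectives describe the group as having severe symptoms that required admission, and criterion 3 uses the same divider against Cohort 2. On that reading hospitalisation is the severity marker. This is a fair reading, and it is why the remedy should not add an oxygen, ICU or ventilation requirement that the protocol never set. It still leaves severe undefined in 4.1 and 5.1.

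For Cohort 4, Section 5.2 already limits the recruitment source to an effective vaccine, so in practice few or no others may enter. That reduces the likely harm, but the selecting criteria and the synopsis still lack the condition, and 5.2 words it differently from 5.1.

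The study is exploratory and descriptive, and Section 9.2.2 plans to explore COVID-19 history and vaccination status. Oxygen, ICU and ventilation data allow Cohort 3 to be described by severity afterwards. This stands for Cohort 3. It does not help Cohort 4, where two of the three items are not collected. A hospitalised vaccinee could also fit the Cohort 3 wording and be asked there, but the protocol gives no rule of precedence.

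A reader might also infer that criterion 3 should demand a minimum interval between dose and infection. Section 5.1 asks only for infection after vaccination, so no such condition has been lost, and an interval taken from the parent vaccine trials would rest on documents not at hand.

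**Conclusion.** The inconsistency is confirmed on the text alone. Criterion 3 omits the effective-vaccine condition of 5.1 for Cohort 4. It also admits to Cohort 3 on hospitalisation alone while 4.1 and 5.1 call that cohort severe. The ICU and ventilation items are not collected for hospitalised participants enrolled in Cohort 4, and analysis cannot recover them later.

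The size is unknown. The protocol does not show how many of the roughly 100 people in either cohort would be affected. A reader might conclude that the severity and vaccination contrasts are understated. The documents do not support that as a statement of fact: dilution of Cohort 3 towards Cohort 2 is possible, but it needs non-severe admissions to be present and to have lower Long-COVID frequency, and the figures above are assumed. Nor do they support saying that unprotected vaccinees will be enrolled, given Section 5.2. The point is a modest one of definition and data capture, worth correcting because the labels will carry the interpretation.

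**What to change.** Reconcile the synopsis and Sections 4.1, 5.1, 5.2 and 5.3.1 as follows.

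- **Cohort 4:** add to criterion 3 the condition in 5.1 that the vaccine has been shown effective against severe COVID-19, use the same wording in 5.2, and record the vaccine product at screening.
- **Cohort 3:** keep all admissions as criterion 3 has them, label the cohort hospitalised throughout, and report its endpoints also by oxygen, ICU and ventilation status.
- **Section 7.1.2.2:** ask the ICU and ventilation items of every hospitalised participant, whatever the cohort.

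The cost is criterion wording, a product field and a changed skip rule in the eCRF, with a few extra entries. The eligible pool for Cohort 4 may be slightly smaller. Nobody is excluded from Cohort 3, and the planned 100 per cohort is unchanged.
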